5.1	SCREENING AND MONITORING EVALUATIONS AND MEASUREMENTS	22
5.1.1	Medical Record Review	22
5.1.2	Other Evaluations, Measures	22
5.2	EFFICACY EVALUATIONS	28
5.3	SAFETY EVALUATION.....	28
6	STATISTICAL CONSIDERATIONS.....	28
6.1	PRIMARY ENDPOINT	28
6.2	SECONDARY ENDPOINTS	29
6.3	STATISTICAL METHODS.....	29
6.3.1	Baseline Data	29
6.3.2	Safety Analysis	29
6.4	SAMPLE SIZE AND POWER	29
7	STUDY MEDICATION (STUDY DEVICE OR OTHER STUDY INTERVENTION)	31
7.1	DESCRIPTION.....	31
7.2	FBT.....	31
7.3	CRT	31
7.3.1	Treatment Compliance and Adherence	31
8	SAFETY MANAGEMENT	32
8.1	CLINICAL ADVERSE EVENTS	32
8.2	ADVERSE EVENT REPORTING	32
8.3	MEDICAL EMERGENCIES	32
9	STUDY ADMINISTRATION	33
9.1	TREATMENT ASSIGNMENT METHODS.....	33
9.1.1	Randomization	33
9.1.2	Blinding	33
9.2	DATA COLLECTION AND MANAGEMENT	33
9.2.1	Data sharing	33
9.3	CONFIDENTIALITY	34
9.4	REGULATORY AND ETHICAL CONSIDERATIONS.....	34
9.4.1	Data and Safety Monitoring Plan	34
9.4.2	Risk Assessment	35
9.4.3	Potential Benefits of Trial Participation	36
9.4.4	Risk-Benefit Assessment	36
9.5	RECRUITMENT STRATEGY	36
9.6	INFORMED CONSENT/ASSENT AND HIPAA AUTHORIZATION	37
9.6.1	Waiver of Assent	38
9.7	PAYMENT TO SUBJECTS/FAMILIES	38
9.7.1	Reimbursement for travel, parking and meals	38
9.7.2	Payments to parent for time and inconvenience (i.e. compensation)	38
9.7.3	Payments to subject for time, effort and inconvenience (i.e. compensation)	39
9.7.3	Gifts	39
10	PUBLICATION.....	39
11	REFERENCES	39

ABBREVIATIONS AND DEFINITIONS OF TERMS

ABSTRACT.**Context:** (Background)

Anorexia nervosa (AN) is a severe psychiatric condition; the hallmark features are low body weight and difficulties gaining weight. Family based treatment (FBT) is the most effective treatment; however, only 50% of adolescents improve. Cognitive Remediation Therapy (CRT) may augment treatment and improve outcome. The best way to add CRT to FBT remains understudied.

Objectives: (primary and important secondary objectives)

The primary objectives include determining whether or not Cognitive Remediation Therapy (CRT) can increase set-shifting in parents and/or adolescents with Anorexia Nervosa (AN). The second objective is to determine the appropriate dose of CRT needed to achieve positive change in set-shifting.

Study Design:

Randomized controlled trial with three groups.

Setting/Participants:

Participants will be 60 adolescents with AN and their families. Treatment will occur on an outpatient basis at Children's Hospital of Philadelphia.

Study Interventions and Measures:

All adolescents with AN enrolled in the trial will receive FBT. Families will be randomized to FBT only, Family Based Treatment + Parent Focus Cognitive Remediation Therapy, or Family Based Treatment + Adolescent Focused Cognitive Remediation Therapy. Psychosocial, neurocognitive, and behavioral measures will be collected throughout the study.

TABLE 1: SCHEDULE OF STUDY PROCEDURES

Study Phase	Screening	Treatment/Intervention																		3- and 6-month follow-ups and 12 optional FBT sessions	
		0	1	2	3	4	5	6	7	8	9	10	11	12	13	14	15	16	17	18	
Visit Number	Assessment	1			2					3				4					5	6	7
Informed Consent/Assent		X																			
Review Inclusion/Exclusion Criteria	X	X																			
Medical Chart Review		X	X	X	X	X	X	X	X	X	X	X	X	X	X	X	X	X	X	X	
Height and Weight		X	X	X	X	X	X	X	X	X	X	X	X	X	X	X	X	X	X	X	
2D:4D measurement		X																			
Treatment			X	X	X	X	X	X	X	X	X	X	X	X	X	X	X	X	X	X	
Questionnaire Battery																					
BRIEF-2 [#]		X								X				X					X	X	X
ABOS [§]		X				X				X				X					X	X	X
AESED [§]		X			X					X				X					X	X	X
EDE-Q*		X			X					X				X					X	X	X

BIS/BAS [#]		X			X				X				X			X		
BASC-3 [#]		X			X				X				X			X		
ECI [§]		X			X				X				X			X		
IUS [#]		X			X				X				X			X		
OCI [#]		X			X				X				X			X		
DFLEX [#]		X			X				X				X			X	X	X
FamQ [§]		X			X				X				X			X		
DASS [#]		X			X				X				X			X		
EDFLIX*		X			X				X				X			X	X	
SRQ*		X			X				X				X					
AQ [#]		X			X				X				X					
CEQ [#]		X																
WAI [○]					X				X				X			X		
TEQ [#]																X		
PVA		X			X				X				X			X	X	X
Neurocognitive Assessment																		
WASI [#]		X														X	*	
RCFT [#]		X							X				X			X		
DKEFS [#]		X							X				X			X		
LBT*		X							X				X			X		
Buffet Challenge*		X											X			X		
Howe's Grocery [§]		X											X			X		
AAT [#]		X			X				X				X			X		

§Parent only completes this measure

*Adolescent only

Parents and Adolescent complete this measure

∞ Parent, adolescent, and therapist complete this measure

.

.

.

.

.

.

.

.

.

.

.

.

.

.

.

.

.

.

.

.

.

.

.

.

.

.

.

.

.

.

.

.

.

.

.

.

.

.

.

.

.

.

.

.

.

.

.

.

.

.

.

.

.

.

.

.

.

.

.

.

.

.

.

.

.

.

.

.

.

.

.

.

.

.

.

.

.

.

.

.

.

.

.

.

.

.

.

.

.

.

.

.

.

.

.

.

.

.

.

.

.

.

.

.

.

.

.

.

.

.

.

.

.

.

.

.

.

.

.

.

.

.

.

.

.

.

.

.

.

.

.

.

.

.

.

.

[figure not shown]
.

.

.

.

FIGURE 1: STUDY DIAGRAM

1 BACKGROUND INFORMATION AND RATIONALE

Anorexia Nervosa (AN) is a serious eating disorder characterized by restriction of food intake and reduction of body weight below what is healthy or expected for someone of the same age and height. AN has the highest mortality rate of all psychiatric disorders^{1,2} and is associated with significant morbidity.¹ AN often begins during adolescence³ and early intervention is key in order to prevent a chronic, unremitting course of the disorder.⁴ To date, there is only one intervention with substantial empirical support for the treatment of AN in adolescents: Family Based Treatment.^{5,6} In FBT, parents are essential to treatment and are charged with the task of re-nourishing their starving child. The effectiveness of FBT has established the importance of the family in treatment and empowered parents to play an active role in treatment.^{7,8}

Studies in adults⁹⁻¹² and adolescents¹³⁻¹⁶ with AN indicate that they have reduced behavioral flexibility (e.g., extreme perfectionism, perseveration, difficulties in learning new behaviors)¹⁷ that reflects underlying neurocognitive inefficiencies, specifically set shifting.¹⁸⁻²⁰ Set-shifting is the ability to switch tasks, change mindsets, rapidly adapt to new situations, and respond to new environmental contingencies.²¹ The evidence of set-shifting difficulties in adults with AN is robust enough that it is considered a putative endophenotype.^{18,22} Endophenotypes are intermediate phenotypes that must be associated with an illness, be present within the individual regardless of the state of the illness, and are inherited. They are found in family members of the proband at a higher rate than in the population and within the family the illness and endophenotype are inherited together (co-segregate).²³ Set-shifting inefficiencies in AN do not fully improve with re-nourishment.²⁴ Similar inefficiencies are found in siblings and parents of individuals with AN.^{18,25-27} Executive functioning is heritable²⁸ and there is preliminary evidence of co-segregation of cognitive inefficiencies in the context of AN.²⁶ If set-shifting difficulties are an endophenotype - parents of adolescents with AN have a greater likelihood of having cognitive inefficiencies that may be exacerbated by the stress of caring for an ill child. Increased difficulties in set-shifting could lead to greater difficulty implementing FBT at home and poorer or less rapid gains for their child. Cognitive Remediation Therapy (CRT) is an adjunctive treatment that improves cognitive flexibility and can be used with the parents or child.

Via structured input and repetition, CRT leverages the brain's natural neuroplasticity and fosters changes in brain structure and connections. CRT can be restorative (focusing on decreasing cognitive inefficiencies), compensatory (maximize daily functioning without changing cognitive impairments), or metacognitive (monitoring one's own thinking and subsequently adapting behavior to the environment).²⁹ CRT for AN is metacognitive. The goal of CRT is to target a cognitive inefficiency using principles of learning in order to improve functional outcomes (i.e., improving memory in traumatic brain injury (TBI) significantly improves the probability of a return to work).³⁰⁻³² CRT has a long history of improving aspects of executive functioning leading to positive impacts on behavior across a number of conditions (including, TBI³³ depression,^{31,34} schizophrenia,^{35,36} and eating disorders^{37,38}). Recent work in AN indicates that CRT can improve eating disorder quality of life and may have a positive impact on weight gain.^{39,40} CRT addresses many characteristics of adolescents with AN that can make treatment more difficult.

CRT for AN has an unambiguous target: cognitive flexibility. By improving this important aspect of a broader system, treatment gains can be maximized. Augmenting treatment with CRT

can potentially strengthen inherited inefficiencies and/or prevent the worsening of neurocognitive abilities due to prolonged malnourishment. Alternatively, as parents are the primary implementers of treatment, targeting their cognitive flexibility can increase their ability to (behaviorally) flexibly respond to contingencies in the environment and implement behavioral plans with their sick child. In turn, parents may be able restore their child's weight more quickly and with a diet that is more macronutrient varied. Increasing flexibility in either the parent or child can impact a larger system of behaviors and lead to improved clinical outcome, including more a macronutrient varied diet and subsequent increase in rate of weight gain.

1.1 Introduction

Augmenting FBT with CRT has the potential to impact the rate at which adolescents gain weight. While the vast majority of research has focused on CRT for adolescents, we propose that it may be more impactful to target the adolescent with AN's parents as parents are the individuals carrying the burden of treatment and re-nourishment of their child. Parent only modifications of FBT are effective in increasing weight in adolescents with AN,⁴¹⁻⁴³ thus a parent focused intervention can be effective.

The purpose of this project is to establish that CRT can move the target of flexibility. The goal is to determine whether or not flexibility improves more in the parent or the adolescent and what dose of CRT is needed to achieve gains in flexibility.

1.2 Name and Description of Investigational Product or Intervention

1.2.1 Family Based Treatment (FBT)

FBT is a manualized family treatment for adolescents with AN. It is effective for children and adolescents aged 12-18. It is a conjoint family treatment with all family members attending all sessions. For this study, we will use a 15 session version of FBT used in prior research. The goal of treatment is weight restoration and reduction of eating disorder symptoms. The primary focus of treatment sessions is to activate and empower the parents of the affected child to restore weight. Secondary goals of FBT include aligning the parental and sibling subsystems and reestablishing healthy adolescent developmental trajectories. Treatment will occur weekly at the beginning of treatment, move to bi-weekly, and then monthly for the last month of treatment. Families will have the option of receiving 12 additional FBT sessions after completing the first 15 sessions. These 12 sessions will be scheduled as families see fit and will occur over the course of six months.

The treatment takes place over 3 phases:

1. Refeeding and Weight Restoration
2. Returning Control of Eating to the Adolescent
3. Addressing Adolescent Issues and Treatment Completion

The PI has received training in the manual and has recently completed the necessary hours for certification in this treatment modality.

1.2.2 Cognitive Remediation Therapy

CRT is an adjunctive intervention focusing on the development of meta-cognition – teaching individuals to think about how they think.⁴⁴ It involves presenting individuals with a variety of

tasks requiring increasingly complex mental abilities – these include geometric figures, illusions, reversing sequences of numbers and letters, completing sorting tasks wherein the rules change, and finding various routes on a map.⁴⁵ Most importantly, CRT focuses on process instead of outcome. That is, instead of focusing on whether or not a task was accurately completed, individuals in CRT are asked to think about how they solved a puzzle, reflect on their thought processes, and identify steps in problem solving. CRT has three goals:

1. Improve brain function by exercising and increasing connections in the brain
2. Encourage individuals to think about their thinking style
3. Encourage individuals and families to spend time away from thinking about the eating disorder.

CRT can be delivered in individual, family, and group formats.⁴⁶⁻⁴⁸ For this study, we will administer CRT to either adolescents or their parents. CRT will be delivered for 45-60 minutes prior to FBT sessions for a total of 15 sessions. Participants in CRT will be given weekly homework.

1.3 Relevant Literature and Data

Anorexia Nervosa (AN) is a life-threatening disorder with a significant impact on the quality of life of those afflicted. Age of onset is typically during adolescence; it significantly alters patterns of healthy growth and development in adolescents and can impact the functioning of the entire family. Severe starvation during the critical period of adolescence affects all developing systems, especially brain development. Results from longitudinal studies of brain function in adults with AN indicate that sufferers have long term difficulties with executive functioning and demonstrate behavioral rigidity (e.g., perseveration, extreme perfectionism, difficulties in learning new behaviors) that reflects underlying neuro-cognitive deficits.^{18,49} These underlying difficulties in executive functioning could be indicative of underlying traits that create of vulnerability to developing AN, they could be the result of starvation during a critical period, or they could be a marker for those who are likely to have a more chronic course of the disorder. Regardless as to whether or not they are a cause or consequence of AN, it is likely that behaviors associated with neurocognitive deficits can maintain AN or interfere with treatment. Thus, addressing executive functioning, specifically that related to flexibility may have a positive impact on treatment outcome. Cognitive Remediation Therapy for AN was developed to do just that.

Evidence for CRT in adolescents. CRT has been successfully developed for adolescents and for administration during a hospital stay.⁵⁰ CRT has been proposed as a viable pre-intervention or adjunct to other forms of treatment.³⁹ It increases cognitive flexibility in adult and adolescent patients with AN.^{38,51,52} For adolescents with AN, CRT is generally well received and can result in increased motivation to engage in treatment.⁵² Parents report feeling as if the rationale for CRT helps them understand their child's behavioral difficulties.⁵⁰ A family-based form of CRT for adolescents with AN facilitated parents' ability to recognize their own and their child's thinking style and helped the family to develop strategies to cope with these thinking styles.⁵² CRT is generally well received by patients and parents, may increase treatment retention, and has a demonstrated impact on executive functioning.⁴⁴ Despite preliminary positive findings, research on CRT in adolescents is limited.³⁸ The dearth of research in this area is a significant gap in our knowledge regarding how best to apply CRT.

Augmenting FBT with *CRT for parents* may impact weight more. Inefficiencies in cognitive flexibility are likely inherited; thus, it is reasonable to assume that parents may also struggle with flexibility. Prolonged stress (such as having a child with a potentially lethal illness) can decrease flexibility and narrow behavioral repertoires in face of threat.⁵³⁻⁵⁵ Parents who have cognitive inefficiencies in the area of set shifting *and* who are tasked with caring for an acutely ill child may struggle with being flexible in the moment. If parents of an adolescent with AN do not have cognitive inefficiencies, they likely experience a state-based reduction in flexibility. Whether state, trait, or combination of both – difficulties in cognitive and behavioral flexibility can translate into more difficulties implementing exposure to symptom specific stimuli and greater symptom accommodation which leads to less macronutrient variation and a slower rate of weight gain. Given that parental control of eating is a strong predictor of weight gain,⁵⁶ augmenting treatment with CRT to maximize their ability to do so has the potential to increase the number of adolescents who reach remission.

The purpose of this study is to further investigate the role of CRT in the treatment of adolescent AN. The goal of this study is to determine whether or CRT increases flexibility in adolescents or parents, if this increase is more than what is observed in FBT alone, and what the dose of CRT is needed to increase flexibility.

1.4 Compliance Statement

This study will be conducted in full accordance all applicable Children's Hospital of Philadelphia Research Policies and Procedures and all applicable Federal and state laws and regulations including 45 CFR 46, and the Good Clinical Practice: Consolidated Guideline approved by the International Conference on Harmonization (ICH). All episodes of noncompliance will be documented.

The investigators will perform the study in accordance with this protocol, will obtain consent and assent, and will report unanticipated problems involving risks to subjects or others in accordance with The Children's Hospital of Philadelphia IRB Policies and Procedures and all federal requirements. Collection, recording, and reporting of data will be accurate and will ensure the privacy, health, and welfare of research subjects during and after the study.

2 STUDY OBJECTIVES

The purpose of the study is to determine whether or not augmenting FBT with CRT for parents or adolescents significantly improves cognitive flexibility and the dose required to do so.

2.1 Primary Objective (or Aim)

Aim 1: To identify whether or not it more impactful to add a parent or adolescent component of CRT to standard FBT. We hypothesize that both adolescents and parents who receive CRT will have greater increases in cognitive flexibility than those who receive FBT alone. We will examine magnitude of change in cognitive flexibility across groups.

Aim 2: To determine the dose of CRT needed to lead to a medium effect size (increase in cognitive flexibility). We will examine the dose of CRT needed to obtain an increase in cognitive flexibility equal to a medium effect.

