6 STATISTICAL CONSIDERATIONS

6.1 Primary Endpoint

Aim 1: To identify whether or not it more impactful to add a parent or adolescent component of CRT to standard FBT. To assess if CRT engages the target, we will use mixed 3 (treatment) x 2 (time) Multivariate Analysis of Covariance (MANCOVA): one for adolescents, one for mothers, and one for fathers. The covariate for all analyses is total IQ on the WASI. Dependent variables are as follows: Trails Number-Letter Sequencing, Inhibition, Inhibition/Switching, Correct Response Shifting, Category Switching, or Description 1 or 2 and Shift on the BRIEF-2. We will follow these steps:

1. Conduct omnibus MANCOVA and evaluate significance. If not significant, stop and move to next analysis.
2. If the omnibus test is significant, we will conduct individual 2 (treatment) X 2 (time) Analysis of Covariance (ANCOVA) to determine which dependent variable had significant change, with IQ again as the covariate.
3. Each assessment of the target (DV) will be examined. Results will inform the Go/No-Go Decision as described in Table 6.

These three steps will be repeated for adolescents, mothers, and fathers. We will include all three groups in the initial MANCOVA and follow-up with planned comparisons (ANCOVA) of FBT vs the appropriate CRT condition. In all analyses, we will focus on the within and between-group effects, examining interaction effects are not necessary to evaluate the target. As we have chosen measures demonstrated to change with CRT,^{40,87-90} we will maintain $\alpha=0.15$ for each analysis.⁹¹ We do not expect adolescents whose parents receive CRT or parents whose adolescents receive CRT to demonstrate increases in flexibility. However, should the planned ANCOVAs not be significant, we will be able to explore other possible group differences. Additionally, we will explore the relationship between dependent variables via discriminant analysis. These additional methods to examine the data will not factor into the Go/No-Go decision, but will enhance the depth of our understanding of the data and contribute to our understanding of neurocognition in AN.

Aim 2: To determine the dose of CRT needed to lead to a medium effect size. Some research indicates that ≥ 8 sessions of CRT are necessary for improvement in cognitive flexibility with AN.⁹² It is unknown how many sessions will be needed for significant change in parents of

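### Aim 1 asks whether CRT does more for parents or for adolescents, but the planned analyses are separate by role and never estimate that difference

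*Combined protocol and SAP*

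**What the plan says.** Section 2.1 states Aim 1 as "To identify whether or not it more impactful to add a parent or adolescent component of CRT to standard FBT". Section 1.1 puts the same question in other words: "The goal is to determine whether or not flexibility improves more in the parent or the adolescent". Section 6.1 repeats the aim at the head of the primary analysis.

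The hypothesis under Aim 1 is different. It is that "both adolescents and parents who receive CRT will have greater increases in cognitive flexibility than those who receive FBT alone", which compares each recipient group with FBT, not parents with adolescents. Section 2.1 then adds: "We will examine magnitude of change in cognitive flexibility across groups".

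Section 6.1 specifies three MANCOVAs, "one for adolescents, one for mothers, and one for fathers". Each stops if its omnibus test is not significant; otherwise ANCOVAs follow, with alpha held at 0.15 for each analysis. "These three steps will be repeated for adolescents, mothers, and fathers". On the contrasts: "We will include all three groups in the initial MANCOVA and follow-up with planned comparisons (ANCOVA) of FBT vs the appropriate CRT condition". The section also says that "examining interaction effects are not necessary to evaluate the target". Other group differences may be explored if the planned ANCOVAs are not significant, and these do not enter the Go/No-Go decision.

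**The concern.** The aim compares two gains: CRT_P over FBT in parents, and CRT_A over FBT in adolescents. Answering it needs an estimate of the difference between those gains, with its uncertainty. Section 6.1 fits no model that joins the roles. The three-arm omnibus test does not fill the gap, because each one compares people of a single role across arms and never sets the parents' gain against the adolescents' gain.

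One role significant and another not is weak evidence that the two effects differ. With small arms it happens often when they are identical. If the trial is read for guidance on who should receive CRT, the only inferential output that the plan specifies could point to one recipient by chance.

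**Working it through.** **Inputs from the documents.** About 60 enrolled and at least 45 evaluable (section 3.3.2); three arms; 15 per group (section 6.4, Aim 2); alpha 0.15, medium effect f = 0.25 and correlation 0.3 between the two time points (section 6.4).

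**Assumptions.** Two-sided tests (sidedness is not stated); one outcome per role; equal true effects of 0.5 SD (f = 0.25 for two groups); correlation between family members' scores of 0 to 0.3.

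**The plan's own figures.** 45/60 = 0.75, so a 25% loss is implied, and 45/3 = 15 per arm agrees with section 6.4. The supplied text gives no power figure for Aim 1, so there is none to reproduce.

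**Step 1: power for one role, 15 v 15.**
- Change score: SD = √(2 × (1 − 0.3)) = 1.183; SE = 1.183 × √(2/15) = 0.432; 0.5/0.432 = 1.157.
- Baseline-adjusted: SD = √(1 − 0.3²) = 0.954; SE = 0.954 × √(2/15) = 0.348; 0.5/0.348 = 1.435.
- Noncentral t, 28 df, critical value 1.480: power p = 0.386 and 0.490.

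**Step 2: how often the verdicts disagree when the effects are equal.** The independent-roles column uses these formulas:
- exactly one of two roles significant: 2p(1 − p)
- three roles not unanimous: 1 − p³ − (1 − p)³
- parent only (mother or father significant, adolescent not): (1 − p)(1 − (1 − p)²)
- adolescent only: p(1 − p)²

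With a within-family correlation of 0.3, the adolescent and parent estimates share only the FBT families and so correlate at 0.3/2 = 0.15. Mother and father estimates share both arms and correlate at 0.3. That column is from 1,000,000 simulated trials.

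| | Independent roles | Within-family 0.3 |
|---|---|---|
| One of two roles | 0.474 to 0.500 | 0.434 to 0.455 |
| Three roles disagree | 0.711 to 0.750 | 0.631 to 0.659 |
| Parent only | 0.377 to 0.382 | 0.331 to 0.335 |
| Adolescent only | 0.127 to 0.145 | 0.128 to 0.139 |

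**Step 3: a more favourable power.** A 2 × 2 group-by-time F test with 30 people and f = 0.25 has λ = 30 × 0.25² × 2/(1 − 0.3) = 5.36 and power 0.80. This is a larger effect than in step 1: √5.36 × 0.432 = 1.0 SD difference in change. Even so, two independent roles disagree in 2 × 0.80 × 0.20 = 32% of trials.

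**Step 4: precision of the missing contrast.** With one parent per family, score variance v and within-family correlation ρ, the variance is 4v/15 − 2ρv/15.
- Baseline-adjusted (v = 0.91): SE 0.493 at ρ = 0 and 0.454 at ρ = 0.3.
- Change score (v = 1.4): SE 0.611 and 0.563.
- 95% half-width (1.96 × SE): 0.89 to 1.20 SD.

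If mother and father are averaged, the variance becomes v(3 − ρ)/15. The SE is then 0.40 to 0.53 and the half-width 0.79 to 1.04 SD, in single-parent SD units.

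**The case against.** The strongest reply is that section 6.1 is about target engagement. The purpose in section 2 and the hypothesis in section 2.1 both ask whether CRT improves flexibility in its recipients, and role-by-role tests against FBT suit that. On this view the fault is loose wording of the aim. This stands in part and is why rewording the aim is an acceptable remedy. But the comparative wording appears in sections 1.1, 2.1 and 6.1, and section 9.4.3.1 again asks who benefits most, so it is not a slip in one place.

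A reader might infer that the plan will decide which recipient benefits more by seeing which p-value falls below 0.15. The documents do not say so: section 2.1 names magnitude of change as something to examine, and no passage states a rule for comparing roles. A reader might also infer that a chance preference would drive the Go/No-Go decision. That rule is in Table 6, which is not in the supplied text, and sections 6.1 and 10 describe the decision in terms of change in the target. No claim about it is made here.

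The disagreement rates also have limits. 2p(1 − p) cannot exceed 0.50, and power of 0.39 to 0.49 lies near that peak. They model one outcome per role, whereas the plan has a gated multivariate test followed by several outcomes. They show the size of the problem and are not operating characteristics of the full procedure.

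**Conclusion.** The point holds in this form: the visible text gives no estimand, contrast or interval for the comparative question in Aim 1, and the inference it does specify cannot answer that question. With equal effects of 0.5 SD and 15 per arm, exactly one of two roles is significant in about 43% to 50% of trials, and the three verdicts disagree in about 63% to 75%. Having two parent tests and one adolescent test tilts isolated significance towards parents by more than two to one. These figures rest on two-sided tests, a single outcome per role and an assumed within-family correlation of 0 to 0.3; at power 0.80 per role, two-role disagreement is 32%. The plan should be corrected, but the separate tests remain valid for the CRT-versus-FBT hypothesis.

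**What to change.** Add one pre-specified contrast to section 6.1: (CRT_P minus FBT in parents) minus (CRT_A minus FBT in adolescents). Specify:
- **Outcome:** one named set-shifting measure given to both parents and adolescents. A D-KEFS score such as Trails Number-Letter Sequencing is a candidate: Table 1 gives the D-KEFS to both, and section 5.1.2.1 says it covers ages 8 to 89. BRIEF-2 Shift is less suitable, as the same section describes that instrument for ages 5 to 18.
- **Scale:** baseline-SD units, with a caution that one SD may not mean the same in parents and in adolescents with AN.
- **Model:** one mixed model with a family random effect.
- **Parents:** a stated rule for combining mothers and fathers, for example averaging.
- **Reporting:** an estimate with a confidence interval, labelled as estimation, and a statement that no claim about which recipient benefits more will be drawn from comparing the separate significance results.

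This needs no new participants, visits or measures, only some analysis work. The cost is candour: the interval will be wide (step 4), so 45 families are unlikely to establish a preference, and the plan should say so in advance. If the sponsor does not want the contrast, the alternative is to reword Aim 1, and the matching sentence in section 1.1, to the separate CRT-versus-FBT questions.
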